4. OBJECTIVES

RESEARCH QUESTION:In adults with medial gastrocnemius injury, how effective is percutaneous electrolysis in terms of pain, kinesiophobia, fatigue and mobility?

HYPOTHESIS:The working hypothesis of the present study is the following: "The application of percutaneous electrolysis (PE) at high intensity (3 mA) and at low intensity (0.3 mA) will be more effective in the treatment of muscle tears of the internal calf than the simulated application of percutaneous electrolysis in adult subjects."

GENERAL OBJECTIVE:To determine the effectiveness of an intervention consisting of the application of percutaneous electrolysis in different doses versus the application of a simulated intervention in adults who present a muscle tear in the internal calf.

SPECIFIC OBJECTIVES:

- 1. To analyze the effectiveness of Percutaneous Intratisular Electrolysis, in its different forms. intensities, applied to the internal gastrocnemius muscle, in terms of myofascial pain in patients participating in the study, both at rest and during muscle contraction, measured using the visual analog scale (VAS).
- 2. To analyze the effectiveness of a simulated intervention applied to the internal gastrocnemius muscle, in terms of myofascial pain in patients participating in the study, both at rest and during muscle contraction, measured through the visual analog scale (VAS).
- 3. Evaluate and compare the effect of the protocols on the level of kinesiophobia of the participating subjects through the TSK-11SV questionnaire.
- 4. To demonstrate whether there are differences in muscle fatigue of the affected muscles of the participants in both groups.
- 5. To objectively determine the degree of range of ankle dorsiflexion mobility with full knee extension of the patients participating in the study.

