The study population for this clinical trial will be completed by a sample of approximately 50 adults between the ages of 18 and 65 who have suffered a muscle injury in the medial gastrocnemius. The researchers will consider a tear in the medial gastrocnemius if this pathology had any of the following characteristics:

- Medical diagnosis of fibrillar tear in the inner calf.
- Physiotherapeutic diagnosis of muscle tear after ultrasound examination.
- Pain in the GM area that coincides with a previously diagnosed fibrillar tear.

Theinclusion criteria for the following study will be the following:

- Age over 18 years and under 65 years.
- Muscle tear in the medial gastrocnemius.
- With pain in the area of the injury.

- That you have been informed of the purpose, as well as the risks and benefits of this study and that you have provided your written consent to participate in the trial.
- Available for tracking.

The exclusion criteria are listed below:

- Active rehabilitation in other musculoskeletal pathology.
- Belenophobia
- Immunosuppression.
- Uncontrolled metabolic diseases.

D) STUDY VARIABLES:

1. Sociodemographic variables

- 1. Age (years).
- 2. Sex.
- 3. Weight (kg).
- 4. Height (m).
- 5. Tear size (cm)
- 6. Location, Since the medial gastrocnemius is a peripheral myoconnective region, we will distinguish between tendon, myotendinous, muscular and myofascial injuries (23).
- 7. Chronicity: This section sets out the time since the rupture occurred. It is considered to be part of the 2nd week if it occurred before 14 days, 3rd week if it occurred before 21 days, 4th week if less than 28 days have passed, and between 4 and 8th week if less than 56 days have passed.

2. Outcome variables.

1. EVA pain scale.

The evaluation of the pain of the participants both in an upright position (without contraction) and in contraction will be carried out through a Verbal Scale

Pain score of 10 points (0 = no pain, 10 = maximum tolerable pain). Subjects will be asked to numerically rate the pain in a neutral standing position and in a position with both heels raised, also commonly known as standing on their toes. In the latter position, a score of 10 will be given if the subjects are unable to maintain this position for at least one full lift.

2. Kinesiophobia questionnaire (TSK-11SV).

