Recovery from painful injuries is associated with fear of movement, also known as kinesiophobia (24). It could be defined as an irrational or excessive fear of movement due to fear of injury or re-injury. For this reason, a kinesiophobia questionnaire (annex II) will be provided at the beginning of the study (day I, evaluation and first intervention) to all participants to assess kinesiophobia of performing certain movements that may cause pain or worsen previous injuries. It consists of 11 questions with a minimum score of 11 and a maximum of 44.

3. Ankle dorsiflexion range with the knee straight.

The evaluation of this variable will be carried out by measuring the angle obtained from the dorsiflexion of the ankle with a knee extension. This stretch is commonly performed in sports practice, so patients are generally already familiar with it...Stretching will be done with participants barefoot.. Likewise, participants will be instructed on how to place the test.. The leg to be tested was positioned so that the foot was placed on the midline of an area marked on the floor, and the foot of the healthy leg was placed forward at a distance of one step. The end point of the gastrocnemius stretch was defined as the point at which participants felt discomfort without lifting the heel and without pelvic rotation. Patients would place their hands against the wall for balance and would be asked to maintain the extended position of the hip and knee joints during the stretch (25).

. .

During the stretch, participants will be instructed to reach a pain or discomfort level of 7 or greater on a scale of 0 to 10 and therefore to hold the stretch at approximately this perceived intensity.

A digital camera (Canon EOS 2000D 24.1 MP) will be placed on the ground at a distance of 2 meters perpendicular to the plane of movement of the right leg to record the standing ankle dorsiflexion angle. The ankle joint angle in stretching will be analyzed by reflective markers placed on the knee (fibular head), ankle (external malleolus) and fifth metatarsal (head) and calculated by free software (RULER- Ergonauts Software. Polytechnic University of Valencia). The maximum standing dorsiflexion is defined as the intersection of a line joining the knee and ankle markers and the horizontal line crossing the heel and fifth metatarsal. (25)

4. Muscle fatigue of the triceps surae.

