The assessment of fatigue in this muscle group will be carried out by performing a heel-raise test (4) at the beginning and at the end of the test for all participants who have completed it. The test consists of placing the patient on one leg and with the help of a metronome at a speed of 40 beats per minute (Garmin Fénix 5/5S), he is asked to raise his heel (4). When the patient is unable to raise his heel for 3 consecutive beats, fatigue will be considered. Light support on a wall is authorized to save the patient's balance.

E) WORK PLAN.

[figure not shown]
The study will be carried out as follows;

- Phase I or initial: Pre-study consultations will begin. Any patient who calls the
 centre to express their wish to take part in the study or who comes to the
 centre naturally will be given an appointment for a consultation with the
 principal investigator. All patients who strictly meet the eligibility criteria will
 be offered to participate in the study.
- Phase II or treatment: The entire treatment will be applied by the same physiotherapist (principal investigator) according to the randomization table that will be made so that each patient is assigned a treatment; high intensity EP, low intensity EP or sham EP. The treatment will be carried out in three sessions divided into three

weeks (days 1, 7 and 14) The person in charge of collecting the data will not be aware of which treatment each patient receives and will collect the data before the interventions.

• *Phase III or evaluation:*Patients will be scheduled for appointments two weeks after the last visit (day 28). The data from this last visit will be collected by the same person as the previous ones. All tests will be performed to collect the data and they will be given a telephone number in case they have any adverse events.

Study timeline.

F) ANALYSIS PLAN

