For the coding and analysis of the data, the SPSS 22.0 statistical program will be used. For the treatment of quantitative variables, tables of absolute and relative frequencies will be prepared; in the case of quantitative variables, frequency measures will be used to determine their distribution, also obtaining their mean and standard deviation. The Kolmogorov-Smimov test will be performed to check the normality of the distribution. For the comparison of means of the continuous dependent variables, a bivariate statistical analysis will be performed using the Student T test. In the case of ordinal dependent variables, a comparison of medians will be performed using the bivariate analysis applying the Mann-Whitney test. In all cases, a 95% confidence interval and a precision error of 5% will be established.

G) LIMITATIONS AND POSSIBLE BIASES OF THE STUDY

This study has a number of limitations that should be taken into account when designing future research.

Firstly, the sample of participants will include people aged between 18 and 82, which may lead to biases due to the different variables that can influence different ages. It should also be noted that all people who participate will do so voluntarily by calling the centre to ask about the study or by showing up at the centre, so the possibility of bias due to voluntary participation must be taken into account.

It should also be noted that only one follow-up consultation will be carried out two weeks after the last intervention, so we will not have information on the behaviour of the variables beyond that date and therefore we will not be able to analyse the long-term results. It would be interesting to add post-intervention evaluations, as well as to study possible long-term recurrences.

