6 DATA COLLECTION SHEETS

DATA COLLECTION SHEET

SOCIODEMOGRAPHIC VARIABLES

Identifier:	Birthdate:
Sex:	Height (m):
Weight (kg):	Chronicity of the injury (weeks):
Location of the lesion:	Tear size (cm):

MYOFASCIAL PAIN VAS SCALE 1-10.

	PRE-INTERVENTION	POST-INTERVENTION
PAIN AT REST		
PAIN IN LOAD		

KINESIOPHOBIA LEVEL

	PRE-INTERVENTION	POST-INTERVENTION
AVERAGE SCORE		

ANKLE DORSIFLEXION RANGE WITH KNEE IN FULL EXTENSION

	PRE-INTERVENTION	POST-INTERVENTION
ANGLE		

MUSCLE FATIGUE OF THE TRICEPS SURAE

	PRE-INTERVENTION	POST-INTERVENTION
TEST SCORE		

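### The analysis plan fixes unadjusted two-sample tests although every outcome has a pre-intervention value, so it probably gives up precision that adjustment would recover at almost no cost

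*Protocol*

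**What the plan says.** Section 5, part F of the protocol names two methods for comparing outcomes. For continuous outcomes it says "comparison of means of the continuous dependent variables, a bivariate statistical analysis will be performed using the Student T test". For ordinal outcomes, "a comparison of medians will be performed using the bivariate analysis applying the Mann-Whitney test". It mentions no covariate and no other model. It does not say which outcomes count as ordinal, whether the t test is paired or independent, or whether the day-28 value or the change is analysed.

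Baseline values are part of the design:

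- The data collection sheet (section 6) has a "PRE-INTERVENTION" column beside a post-intervention column for pain at rest, pain in load, kinesiophobia, dorsiflexion angle and the fatigue test.
- The kinesiophobia questionnaire "will be provided at the beginning of the study (day I, evaluation and first intervention").
- The work plan (part E) has the assessor collect data before the interventions. At the day-28 visit, "All tests will be performed to collect the data".

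The general objective (section 4) is comparative: electrolysis "in different doses versus the application of a simulated intervention". The study population (part C) is "a sample of approximately 50 adults", in three parallel groups.

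**The concern.** Pain, kinesiophobia, ankle range and heel-raise performance differ between people before treatment starts, and part of that difference usually persists to day 28. A test that ignores the pre-intervention value leaves this variation in the error term. A linear model with the pre-intervention value as covariate removes it.

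The trial is small. If about 50 people are split equally over three arms, each active-versus-sham contrast rests on about 34. With so few, wide intervals are the main risk to a useful answer, and the information that would narrow them is already on the collection sheet.

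**Working it through.** The protocol states no power, effect size, SD or correlation, so there is no figure of its own to reproduce. The calculation compares three analyses under common assumptions.

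**From the protocol:** three arms, about 50 participants, 5% error level.

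**Assumed:** equal allocation with 17 per arm (3 × 17 = 51), no dropout, normal outcomes, equal SD before and after, a true difference of 0.8 SD, a two-sided test, one active-versus-sham contrast with no multiplicity adjustment, and pre-post correlation r of 0, 0.3, 0.5 or 0.7.

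**Variance of the arm difference, relative to a t test on day-28 values:**

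- day-28 t test: 1
- change-score t test: 2(1 − r)
- analysis of covariance: 1 − r², times a small factor for estimating the slope (1 + 1/30 with two arms, 1 + 1/46 with three)

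**Power** comes from the noncentral t distribution with noncentrality 0.8 / √(2v/17), where v is the relative variance. Worked values:

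- Day-28 t test, v = 1: 0.8 / √(2/17) = 2.33 on 32 df, power 0.619.
- Two-arm analysis of covariance at r = 0.5: v = 0.75 × 1.033 = 0.775, noncentrality 2.33 / √0.775 = 2.65 on 31 df, power 0.728.

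| Analysis | r = 0 | r = 0.3 | r = 0.5 | r = 0.7 |
|---|---|---|---|---|
| t test, day-28 value (32 df) | 0.619 | 0.619 | 0.619 | 0.619 |
| t test, change score (32 df) | 0.360 | 0.481 | 0.619 | 0.831 |
| Analysis of covariance, two arms (31 df) | 0.604 | 0.644 | 0.728 | 0.875 |
| Analysis of covariance, three arms (47 df) | 0.618 | 0.659 | 0.742 | 0.886 |

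Like for like (two arms), adjustment changes power by about −1.5, +2.5, +11 and +26 points against day-28 values, and by about +24, +16, +11 and +4 points against change scores. The three-arm model's further point or so comes from pooling the variance over three arms, not from the baseline: three arms without baseline give 0.628.

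**Half-width of the 95% confidence interval, in SD units:**

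| Analysis | r = 0 | r = 0.3 | r = 0.5 | r = 0.7 |
|---|---|---|---|---|
| Day-28 value | 0.70 | 0.70 | 0.70 | 0.70 |
| Change score | 0.99 | 0.83 | 0.70 | 0.54 |
| Analysis of covariance, two arms | 0.71 | 0.68 | 0.62 | 0.51 |

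A separate simulation of 20,000 two-arm trials per correlation gave 0.608, 0.648, 0.722 and 0.873 for analysis of covariance, in line with the formula. With 14 per arm the pattern is the same: day-28 t test 0.531; two-arm analysis of covariance 0.514, 0.552, 0.634 and 0.797.

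**Pain ratings.** The figures above do not carry over directly to 0-10 integer scores, so these were simulated (20,000 trials per cell, 17 per arm). Further assumptions: a normal score rounded and clipped to 0-10, pre-intervention mean 5.5, sham day-28 mean 4.0, SD 2.2, shift 0.8 SD.

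| Analysis | r = 0 | r = 0.3 | r = 0.5 | r = 0.7 |
|---|---|---|---|---|
| Mann-Whitney, day-28 rating | 0.593 | 0.598 | 0.586 | 0.590 |
| Mann-Whitney, change | 0.323 | 0.430 | 0.541 | 0.742 |
| Quade's rank-based analysis of covariance | 0.585 | 0.623 | 0.679 | 0.820 |

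The pain variable has a special rule for the heel-raise position: "a score of 10 will be given if the subjects are unable to maintain this position". Setting the top 15% of scores to 10 to mimic it gave 0.583, 0.584, 0.588 and 0.587 for Mann-Whitney on day 28, and 0.575, 0.608, 0.678 and 0.816 for Quade's method. With no true difference, the day-28 Mann-Whitney test rejected in 4.8-5.0% of trials and Quade's test in 4.8-5.2%. Both hold their level, so the difference is in precision alone.

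**The case against.** **The reading is inferred.** Part F does not say that the t test is between groups. Specific objectives 1 and 2 treat electrolysis and the simulated intervention in separate statements, which with a pre/post sheet leaves a within-arm paired test open. If that were meant, the defect would be a missing between-group comparison. The ambiguity stands, but the hypothesis and general objective compare with sham, and Mann-Whitney is a two-sample test, so the between-group reading is the natural one.

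**Baseline may already enter through change scores.** It may. Under that reading adjustment is still better at every correlation shown, though by only about 4 points at r = 0.7. With equal SDs, the adjusted variance is (1 + r)/2 of the change-score variance before the small slope allowance.

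**The gain is uncertain and the tests are valid.** Both are true. Against day-28 values the effect ranges from a small loss to 26 points, depending on an unstated correlation. No bias arises. Covariates are often left to a statistical analysis plan, but here the protocol positively names the tests, so this is a stated choice and not an omission.

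**The remedy has limits.** For pain, an adjusted rank test beside an unadjusted interval means the interval gains no precision and can disagree with the p-value. That stands as a limitation for pain. It does not touch the linear-model remedy for the other outcomes. The protocol also does not define the unit of the heel-raise score, and it limits that test to participants who have completed it, so the score and its baseline need to be pinned down before it is modelled.

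**Conclusion.** The point holds. The protocol fixes covariate-free tests while recording a pre-intervention value for every outcome. Whether day-28 values or changes are compared, a baseline-adjusted analysis is more precise, except when the correlation is near 0 (against day-28 values) or near 1 (against changes).

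At a correlation of 0.5 the gain is about 11 power points against either version. In variance terms, ignoring the slope allowance, that is like having 50 / 0.75 ≈ 67 participants instead of 50 when compared with day-28 values. The worst case found is a loss of about 1.5 points at zero correlation. These sizes rest on the assumed 17 per arm, 0.8 SD effect and equal SDs. The direction depends little on them.

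This is a change the sponsor should make. It is not a flaw that invalidates the trial.

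**What to change.** Rewrite the comparison paragraph in section 5, part F so that each outcome has one named method.

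- **Dorsiflexion angle, TSK-11SV total and heel-raise score:** a linear model of the day-28 value on treatment arm (three levels) and that outcome's own pre-intervention value. Report adjusted differences from sham with 95% confidence intervals. The same model also supplies the high-versus-low-intensity contrast.
- **The two 0-10 pain ratings:** Quade's rank-based analysis of covariance for each active arm against sham, with the pre-intervention rating as covariate. Report the Hodges-Lehmann difference with its 95% confidence interval beside it, and state that this estimate is unadjusted. An ordinal logistic model is less suitable, because an 11-point scale would leave sparse categories with about 50 participants.

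Treating pain as ordinal and the questionnaire total as continuous is a choice made here, because the protocol does not assign outcomes to tests. The sponsor should confirm it.

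The cost is one paragraph and slightly more analysis work, with no new data or visits. Each model spends one degree of freedom. The rank-based method gives no effect size on the 0-10 scale, which is why the separate estimate is needed.

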6 DATA COLLECTION SHEETS

DATA COLLECTION SHEET

SOCIODEMOGRAPHIC VARIABLES

Identifier:	Birthdate:
Sex:	Height (m):
Weight (kg):	Chronicity of the injury (weeks):
Location of the lesion:	Tear size (cm):

MYOFASCIAL PAIN VAS SCALE 1-10.

	PRE-INTERVENTION	POST-INTERVENTION
PAIN AT REST		
PAIN IN LOAD		

KINESIOPHOBIA LEVEL

	PRE-INTERVENTION	POST-INTERVENTION
AVERAGE SCORE		

ANKLE DORSIFLEXION RANGE WITH KNEE IN FULL EXTENSION

	PRE-INTERVENTION	POST-INTERVENTION
ANGLE		

MUSCLE FATIGUE OF THE TRICEPS SURAE

	PRE-INTERVENTION	POST-INTERVENTION
TEST SCORE		

9. ETHICAL CONSIDERATIONS

Participation in this study will be voluntary, anonymous, unpaid. and, in any case, after signing an informed consent form that will be given at the beginning of the treatment. This consent form details all the relevant aspects of this study. No data of the participants can be related to any particular individual, because the results of the study, as well as the data of the participants, will be published in a format that guarantees their absolute confidentiality. All patients will have the opportunity to ask questions. 100% of the participants will be aware of the voluntary nature of the study, as well as that they can leave it at any time without penalty or commitment. This study protocol will be sent for approval by the Salamanca Biomedical Research Institute (IBSAL). The research will proceed according to the Declaration of Helsinki on medical research on human beings, all data will be treated in accordance with the precepts of Organic Law 3/2018 of December 5 on the protection of personal data and guarantees of digital rights.

11. ANNEXES

TSK-11SV QUESTIONNAIRE

Tampa Scale for Kinesiophobia (Spanish adaptation. Gómez-Perez, López-Martinez and (Ruiz-Párraga, 2011)

INSTRUCTIONS: A series of statements are listed in which you have to determine to what extent this occurs according to the following scale:

1 2 3 4
Completely Completely disagree OK

1. I a	nm afraid of getting injured if I exercise	1234
2. If I let myself be overcome by pain, the pain would increase		1234
3. My	body is telling me that I have something serious.	1234
4. Having pain always means that there is an injury		1234
	in the body	
5.	I'm afraid of accidentally injuring myself.	1234
6.	The safest way to prevent further pain is to be	1234
	careful and not make unnecessary movements.	
7.	Pain tells me when I should stop the activity	1234
	to avoid injury.	
8.	It wouldn't hurt so much if I didn't have something	1234
	serious going on in my body.	
9.	It is not safe for a person with my condition to	1234
	do physical activity.	
10. I can't do everything that normal people do 1 2 3 4		
	because I could easily get injured.	
11. N	lo one should do physical activities when	1234
	they are in pain.
